[These Preliminary Studies' data were noted by a couple of the reviewers as 'Approach Strengths' (e.g., "a thoughtful and sequential series of pilot testing of ABMT at their site and with the proposed sample."). In this revision, we have strengthened the pilot data on feasibility further. Specifically, since the prior submission, we received IRB approval to gather pilot data on the randomized controlled trial protocol, not just an open trial. We thus identified and contacted five families and invited them back to CAPP to learn more about this project. Four families agreed to come in and also agreed to random assignment to either ABMT or PC Task. At the time of this submission, two of the youths have completed a pre assessment, eight sessions of PC Task, and a post assessment. One youth has completed a pre assessment, eight sessions of ABMT, and a post assessment. The other case is currently still receiving ABMT. These data lend further support to our ability to successfully carry out the proposed R34 protocol, including random assignment to conditions and participants' full completion of conditions.]

APPROACH

Design

See Figure 3 for the randomized, double blind, placebo controlled design. After a pretreatment (pre) assessment, patients will be assigned randomly to one of two conditions: ABMT or PC Task. In ABMT, patients will complete eight biweekly sessions of ABMT followed by a post assessment. In PC Task, patients will complete eight biweekly sessions of a PC Task followed by a post assessment. After post assessment, no training or assessment will be administered for eight weeks. At that time, patients will come back to our clinic for a FU assessment.

[After the FU assessment, patients in the PC Task condition will be offered ABMT (see Human Subjects).] Total duration of patients' involvement from pre to FU will be about 12-14 weeks. Number and duration of sessions will be identical in both conditions.

Participants

Approximately 70 youth (8-16 years) will be admitted to the study. Based on participant characteristics in R01 MH079943, we expect an even gender distribution. Based on attrition rates in ABMT studies with clinical samples^{33,35,37,42}, we estimate 5-15% attrition from pre to FU, which would yield 60-66 study completers. We

[figure not shown]

Figure 3. Study Design and Assessment Waves.

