Exclusion Criteria. For youth to be excluded, they must (A) meet diagnostic criteria for Organic Mental Disorders, Psychotic Disorders, Pervasive Developmental Disorders, or Mental Retardation; (B) show high likelihood of hurting themselves or others; (C) have not been living with a primary caregiver for at least 6 months who is legally able to give consent for the child’s participation; (D) be a victim of previously undisclosed abuse requiring investigation or ongoing supervision by the Department of Social Services; (E) be involved currently in another psychosocial treatment; (F) have a serious vision problem that is not corrected with prescription lenses; or (G) have a physical disability that interferes with their ability to click a mouse button rapidly and repeatedly. See Human Subjects for more information on study’s exclusion criteria, including the decision to exclude youth involved in another psychosocial treatment.

Treatment Conditions

Patients will be assigned randomly to the two conditions (i.e., ABMT or PC Task). The administration of each session is identical in both conditions and will follow the same standardized protocol. Because all participants who will be enrolled in this R34 participated in R01 MH079943, they already have experience in coming to our clinic. Further details on our clinic setting are provided under Facilities and Other Resources.

General Procedures. Following the prototype of past ABMT trials^{33,35}, patients will complete 15-minute ABMT or PC Task sessions twice a week. Consistent with the modal number and temporal spacing of sessions in past research^{33,35,37}, patients will complete eight sessions spaced over four weeks. In the event that patients

miss scheduled sessions (e.g., due to illness, travel), the length of the treatment period may be extended up to two weeks (for a total of six weeks). To maintain integrity of the study design and FU assessment, treatment will stop after six weeks regardless of how many sessions have been completed. Number of sessions and number of weeks needed to complete sessions will be considered in the analyses (see Data Analysis).

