IV. Acceptability, Feasibility and Maintenance of Blind. Feasibility will be ascertained by recording the number of eligible families who do not enroll their child in the study. Across both ABMT and PC, we will record number of enrolled patients who did not complete the study. We also will record (a) cancelled and missed sessions and (b) weeks needed to complete eight sessions. (A) and (B) will be recorded using the project's session summary forms, which will be completed by the PC and ABMT graduate assistant task administrators at each scheduled session. [name] will review the session summary forms weekly to ensure their full completion. We also will determine maintenance of the blind by asking youth patients and their parents at FU whether they believed the youth was in either the ABMT or PC condition. Research on ABMT has found that most patients believed they were in the PC Task condition³³.

V. Additional Measures

a. Anxiety Disorders Interview Schedule – Child/Parent-IV (ADIS-C/P-IV)¹⁴⁵. As in most youth anxiety CBT trials, youths' anxiety disorder diagnoses will be made using the ADIS-C/P. All youths and their parents (usually mothers, see Human Subjects) will be administered the ADIS-C/P at a pre evaluation to obtain current Axis I diagnoses and determine eligibility for study participation. The ADIS-C/P will be re-administered at post and FU evaluations. [Although diagnostic status is not an outcome variable due to low statistical power given its dichotomous nature, we will report rates of anxiety diagnoses across conditions for descriptive purposes.]

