We appreciate these positive comments about how the project is innovative. In addition, in response to reviewers’ request that we further develop a theory-treatment link, in this resubmission we have further developed this link regarding why some patients do not respond to CBT and why ABMT is likely to help those patients. The innovation of the project has been further enhanced by including attention control as a potential moderator of ABMT’s anxiety reduction effect. This project moves beyond past ABMT studies by collecting data not just on outcome, but also potentially promising mediator and moderator variables contained in our model.]

DATA ANALYSIS

Data management protocols will be used to ensure integrity of the data. Data will be checked for out of range and missing values. Missing data should be minimal. Missing values will be estimated using Markov chain Monte Carlo multiple imputation algorithms based on the Gibbs sampler in the Mplus program¹⁴⁷. Space constraints do not permit us to describe all the details of our analytic approach. We highlight major issues focusing on the Specific Aims. Primary methods of analysis will focus on traditional least squares tests of means as well as modern robust estimation procedures¹⁴⁸ that are outlier resistant, make minimal assumptions about population distributions, and are more powerful than traditional methods¹⁴⁸⁻¹⁵⁰. The latter techniques rely on Wilcox’s R routines¹⁴⁹. Initial analyses will examine associations between condition and baseline variables (i.e., diagnosis, treatment history, demographics, and time since R01 MH079943 FU) to ensure randomization was successful. Table 2 provides a summary of planned analyses. We will compare the robustness of our conclusions with and without statistical corrections for multiple tests¹⁵¹. We will use a Holm adjusted modified Bonferroni method for controlling experimentwise error rates; it is more powerful than traditional Bonferroni or Scheffe methods¹⁵².

Findings on acceptability, feasibility, and maintenance of blind variables will be reported separately for ABMT and PC, as well as the total sample. We will test for differences between ABMT and PC on these variables using independent sample t-tests.

Aim 1: Test whether ABMT produces significantly lower levels of anxiety at post as compared to PC

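### The planned between-arm t-test on weeks to complete eight sessions has no stated rule for youth who never reach session 8; a true arm difference could be understated (minor)

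*Combined protocol and SAP*

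**What the plan says.** Measures, section IV, lists what will be recorded. On enrolment: "Feasibility will be ascertained by recording the number of eligible families who do not enroll their child in the study". On retention: "Across both ABMT and PC, we will record number of enrolled patients who did not complete the study". On attendance: "We also will record (a) cancelled and missed sessions and (b) weeks needed to complete eight sessions". Youth and parents are also asked at follow-up which condition they believe the youth was in.

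Data Analysis then sets the reporting level: "Findings on acceptability, feasibility, and maintenance of blind variables will be reported separately for ABMT and PC, as well as the total sample". The next sentence sets the test: "We will test for differences between ABMT and PC on these variables using independent sample t-tests". No variable is exempted.

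Two design features bear on this. Under Treatment Conditions, General Procedures, the eight sessions are planned over four weeks, with up to two extra weeks for missed sessions, and "treatment will stop after six weeks regardless of how many sessions have been completed". Under Approach, Design, the order of events is: "After a pretreatment (pre) assessment, patients will be assigned randomly to one of two conditions: ABMT or PC Task".

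General Procedures also says that the numbers of sessions and weeks will be taken into account in the analyses and points to Data Analysis. That section gives no rule for either. Its only general provision for absent values is multiple imputation.

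**The concern.** The variable described as "weeks needed to complete eight sessions" exists only for youth who reach session 8. A youth who quits never has a value. A youth stopped at six weeks after, say, seven sessions has a time known only to be longer than six weeks. These are the youth for whom the schedule did not work, and they are the ones a t-test on observed times leaves out. If one arm has more of them, its finishers are a more selected group and the gap between arms looks smaller than it is.

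The Research Overview and Future Plans section makes feasibility data on both tasks part of the study's most important purpose and describes the study as a springboard to a larger trial. A comparison that understates a scheduling problem in one arm would feed into that next design.

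**Working it through.** **Figures in the plan.** No figure is given for the feasibility t-tests. The nearest is expected attrition of 5–15% of 70 youth, stated as 60–66 completers. This reproduces: 70 × 0.85 = 59.5 and 70 × 0.95 = 66.5. So 4 to 10 youth are expected not to complete, counted from pre assessment to follow-up and therefore not all during training. In the pilot open trial (Preliminary Studies), all six families finished eight sessions in four weeks and 1 of 48 appointments was rescheduled.

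**Model (an assumption, not trial data).** There are two session slots per week, so six weeks hold 12 slots. Each slot is attended independently with probability p, and training is complete at the eighth attended slot.

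- P(session 8 falls in slot k) = C(k−1, 7) p^8 (1−p)^(k−8), and weeks = k/2.
- P(cut off) = 1 − the sum of these probabilities over k = 8 to 12.
- Mean weeks with no cut-off = (8/p)/2 = 4/p.
- Mean in finishers = the mean of k/2 given k ≤ 12.
- Mean with cut-off youth scored as 6 = the sum over k ≤ 12 of k/2 × P(k), plus 6 × P(cut off).

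| p | P(cut off) | Expected cut off of 35 | Mean, no cut-off | Mean, scored as 6 | Mean, finishers only |
|---|---|---|---|---|---|
| 47/48 | about 3 in a million | 0.0 | 4.085 | 4.085 | 4.085 |
| 0.9 | 0.4% | 0.2 | 4.444 | 4.442 | 4.435 |
| 0.8 | 7% | 2.5 | 5.000 | 4.940 | 4.857 |
| 0.7 | 28% | 9.7 | 5.714 | 5.397 | 5.167 |
| 0.6 | 56% | 19.7 | 6.667 | 5.725 | 5.371 |

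**Differences between arms, by subtraction.** Power is from 4,000 simulated trials per row, 35 per arm, with a two-sided t-test at 0.05. That level is assumed, since none is stated for these tests.

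| p in the two arms | True difference (weeks) | Scored as 6 | Dropped | Power: true / scored as 6 / dropped |
|---|---|---|---|---|
| 0.9 vs 0.8 | 0.56 | 0.50 | 0.42 | 0.95 / 0.95 / 0.88 |
| 0.8 vs 0.7 | 0.71 | 0.46 | 0.31 | 0.88 / 0.82 / 0.46 |
| 0.7 vs 0.6 | 0.95 | 0.33 | 0.20 | 0.86 / 0.65 / 0.17 |

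Dropping cut-off youth loses (0.556 − 0.422)/0.556 = 24% of the difference in the first row and (0.714 − 0.310)/0.714 = 57% in the second. Scoring them as 6 loses (0.556 − 0.498)/0.556 = 10% and (0.714 − 0.457)/0.714 = 36%. The slower arm still looks slower in every row: this is attenuation, not reversal.

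**Early quitting only.** Let both arms attend at p = 0.9, with nobody quitting early in one arm and 20% quitting in the other. Finishers' means are then identical at 4.43 weeks. Failure to finish is 0.4% in one arm and 1 − 0.8 × 0.9957 = 20.3% in the other. A t-test on weeks among finishers sees nothing; the proportion finishing shows the difference directly.

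**Multiple imputation.** This was not simulated. Filling in times from finishers, without using the fact that the time exceeds six weeks, would be expected to err in the same direction. For a youth who quit there is no true time to recover.

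**The case against.** **The plan does not say that cut-off youth are deleted.** This is right. The Participants section promises intent-to-treat as well as per-protocol analyses, Data Analysis has a multiple-imputation rule, and it states that not all details could be described. The fault is an absent rule, not a stated bad one. It remains a gap, because imputation as described does not fit this variable.

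**Other indicators would show the problem.** Largely true. Non-completion and missed sessions are reported by arm, so it would be wrong to infer that the plan hides the less feasible arm. The cover is partial: a youth stopped short of eight sessions can still attend both later assessments and count as a study completer.

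**The pilot suggests that almost nobody will be cut off.** At pilot attendance the bias is nil for practical purposes. The two arms also run identical, blinded sessions, so no gap between them is expected, and with equal times and equal quitting there is nothing to attenuate. This limits the size of the point. The pilot had only six families, all on ABMT, and the plan itself provides for missed sessions.

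**Two stronger readings are tempting.** A reader might say that non-enrolment makes the planned comparison impossible. Of the 90 eligible youth projected, 70 are expected to enrol, so 90 − 70 = 20 never have an arm. But no analyst could run that test, and the promised total-sample report covers the variable. It is loose wording with no wrong result behind it.

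A reader might also infer that exact tests are needed for the yes/no items (completion, guess of condition). With 0/35 against 4/35 non-completers the t-test gives p = 0.040 and Fisher's exact test p = 0.114. Yet with 35 per arm and event rates of 5–15%, the type I error of the t-test is about 0.04–0.06, so the t-test is not shown to mislead there.

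**Conclusion.** The point holds in a limited form. The plan applies a between-arm t-test to a time that is undefined for youth who quit or are stopped before session 8, and it gives no scoring rule for them. Dropping them or scoring them as six weeks understates a true difference.

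The effect is near zero at pilot attendance. It becomes material only if roughly 7% or more of an arm is cut off or quits and the arms differ. These sizes rest on an assumed attendance model with independent slots; the documents give no attendance figures beyond the pilot. The Aim 1 to 3 analyses are not affected. Severity: minor.

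**What to change.** In Data Analysis, replace the t-test on weeks with one of two comparisons that use every randomised youth:

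- the proportion in each arm who complete eight sessions within six weeks, with the difference and its confidence interval; or
- time to session 8, censored at the six-week stop for youth still attending, with dropouts counted as not completed.

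Keep t-tests for counts that every randomised youth has, such as missed and cancelled sessions. State that non-enrolment is reported for the whole eligible pool only, since it precedes randomisation.

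The cost is a few sentences. The session summary forms are completed at each scheduled session and should supply what is needed, though the team should confirm that they allow session 8 to be dated.

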As noted, [name] is PI of the current clinical trial (R01 MH079943) for approximately 300 youth who meet DSM-IV criteria for SOP, GAD, or SAD. Participants who complete this trial and continue to meet criteria for a primary diagnosis of SOP, GAD, or SAD at post and one year FU will be recruited for the proposed project. As of July 2012, 190 participants have completed R01 MH079943. Table 1 shows the number of participants who have completed R01 MH079943 and the projected number who will complete R01 MH079943 during each 12 month period through the end of the study (including a likely one year no cost extension). Based on preliminary findings from the R01 MH079943 sample and

findings from past youth anxiety CBT trials including [name] et al. trials¹⁻³, we expect 60 to 80% of participants will meet criteria for treatment response. The current response rate among participants who completed R01 MH079943 is 70.4%. Thus, consistent with past work, about 30% of participants who complete R01 MH079943 will meet our operational definition of nonresponder, leading to a total of 90 youth who will be eligible for the R34. Based on our past studies and pilot data (described below), we project that 70 (~77%) families of these 90 youth will provide their consent to participate in the R34. Based on pilot data and attrition rates in ABMT studies with clinical samples^{33,35,37,42}, we estimate about 90% of the 70 youth who enroll in the

Table 1. Schedule of projected R34 enrollment in relation to R01 MH079943 activities.

	2009	2010	2011	2012	2013	2014	2015	Mar 2016
R01 MH079943								
Cumulative n completed trial	22	81	150	210	270	300 (end June)	--	--
R34	--	--	--	--	20 (start April) 12	45	70	70
Cumulative n enrolled in study	--	--	--	--		35	60	63
Cumulative n completed study	--	--	--	--				

R34 will complete the study, leading to a final estimated sample of 63 study completers (final column in Table 1; also see Approach section for details about R34 selection, recruitment, and attrition). The amount of time from R01 MH079943 completion to R34 condition assignment (assuming April 2013 start date) will range from about four years to one month. As described in Data Analysis, we will examine length of time since R01 MH079943 completion and any intervening treatment as covariates, as appropriate.

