will follow all randomized participants so that we can perform per protocol analyses (PP; evaluating participants who complete the study) and intent to treat analyses (ITT; evaluating all participants enrolled regardless of whether they complete the study). ITT is widely used in randomized clinical trials, although some researchers have expressed concern it may underestimate treatment effects and be overly conservative for preliminary efficacy studies¹²²⁻¹²⁴. Conversely, PP may overestimate treatment effects¹²⁴. In light of their advantages and limitations in a pilot study and consistent with guidelines of the International Conference on Harmonisation¹²⁵, we will analyze the data using both approaches and note differences in findings across the approaches.

Recruitment and Selection. All patients who have completed or who will complete the 12-14 week CBT trial in R01 MH079943 and still meet criteria for a primary diagnosis of SOP, GAD, or SAD at post and one year FU will be contacted. We note that among youth patients there is *no* evidence that attention bias differs across type of anxiety disorder^{12,14}. Requirement of a diagnosis at both post and FU ensures the sample consists of youth who do not respond to CBT. If we required a diagnosis *only* at post (not FU), the sample might include youth who have a positive albeit slow response to CBT¹²⁶. Waiting a full year allows sufficient time for beneficial CBT effects to manifest – or more relevant to the R34, *not to* manifest. Conversely, if we required a diagnosis *only* at FU, the sample might include youth who responded to CBT but subsequently relapsed or recurred in the year after CBT. It would be inaccurate to label such youth ‘CBT nonresponders.’ Thus, we view it important to require a primary diagnosis of SOP, GAD, or SAD at both post and one year FU so that we can draw conclusions accordingly with respect to ABMT effects for a clearly defined population.

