Past research on ABMT with adult clinical samples has reported medium to large effect sizes for reductions in anxiety symptoms (Hedge's $d=.78$) and large effect sizes for reductions in attention bias toward threatening stimuli (Hedge's $d=1.16$)³². The extent to which similar effect sizes would be found in the proposed sample of youth who did not respond well to CBT is unknown. In this project, we would like to be able to detect effects of medium size (Cohen's $d=.50$) or larger. For a single degree of freedom contrast between two independent groups, the approximate sample size needed to achieve power of 0.80 for a mean difference of $d=.50$ is 64 per group, a number that exceeds our projected $n=35$ per group.

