Approaches to increasing statistical power in randomized clinical trials generally focus on increasing sample size, but an alternative strategy is to introduce covariates that reduce within-subject error and thereby increase the precision of estimated between-group differences. The latter approach leads to a more sensitive significance test for the treatment effect¹⁵⁷. In the proposed R34, our sample size will be constrained by the number of youth who do not respond to CBT in the current R01 MH079943 study. Thus, we will increase the statistical power available by adjusting for relevant covariates measured at pre. Covariate adjustment for the pre score on each outcome measure will substantially increase statistical power¹⁵⁸. For example, if pre and post scores correlate at $r=.65$ (which seems reasonable based on the test-retest reliability estimates for our outcome measures and preliminary pre to post data from R01 MH079943), then power of 0.80 to detect a mean difference of $d=.50$ is available with a sample size of approximately 36 per group. Our projected sample size of 35 per group maps closely onto this estimate. To increase statistical power further, we will covary [pre attention bias scores] and examine other characteristics measured at pre (e.g., age, gender, diagnosis, R01 MH079943 condition, past treatment, current medication use, number of comorbid diagnoses) to determine whether they differ across conditions. If they vary across conditions, we will include them as covariates which will reduce the "noise" in the estimated treatment effect and thereby increase power. In general, the robust methods of analysis will be as powerful or more powerful than the least squares regression methods, so the power estimates above apply, conservatively, to the robust methods of analysis as well.

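### The power statement compares the required 36 per group with the 35 per group enrolled and leaves out the plan's own 5–15% attrition; completer power for d = .50 is about .71–.75

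*Combined protocol and SAP*

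**What the plan says.** The Statistical Power section sets the target: "we would like to be able to detect effects of medium size (Cohen's $d=.50$) or larger". It gives 64 per group as the requirement without covariates and accepts that this is out of reach. It then argues that adjusting for the pre score at r = .65 cuts the requirement to about 36 per group, and concludes: "Our projected sample size of 35 per group maps closely onto this estimate".

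The 35 per group is full enrolment. About 70 youth are to be admitted (Approach, Participants), and the Aim 1 and Aim 2 contrasts in Data Analysis are written with n = 35 in each condition.

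The plan does not expect outcomes on all 70. Under Participants: "we estimate 5-15% attrition from pre to FU, which would yield 60-66 study completers". Preliminary Studies, with Table 1, puts retention at about 90%, "leading to a final estimated sample of 63 study completers".

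Both a per-protocol analysis of completers and an intent-to-treat analysis of everyone enrolled are planned (Participants). For missing data, Data Analysis says: "Missing values will be estimated using Markov chain Monte Carlo multiple imputation algorithms". The power section also intends to add the pre attention bias score as a covariate, without saying how much variance it would explain.

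**The concern.** A requirement for participants with outcome data is compared with a count of participants enrolled. The plan's own forecast is 30–33 completers per group, yet every calculation in the power section uses 35 per group or N = 70. For the completer analyses, the stated sensitivity to a medium effect is therefore higher than the plan's retention estimate supports.

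The pilot exists to guide a later trial, and the Research Overview says those plans would be modified if the data do not support efficacy. A non-significant result will be read against the stated power, so the figure should match the number expected to be analysed.

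**Working it through.** **Inputs.** From Statistical Power: d = .50, r = .65, target power .80, about 36 per group required, 35 projected. From Participants: 70 enrolled, 5–15% attrition to follow-up, 60–66 completers. From Preliminary Studies: 63 completers. Assumed: two-sided α = .05, which the plan states only for Aim 3. The assumption is supported because an exact two-sided t-test reproduces the plan's 64 per group without covariates.

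**Formula.** For two equal groups with one covariate, the standardised effect after adjustment is .50/√(1 − .65²) = .50/.760 = .658. With N participants who have outcome data, the noncentrality is λ = .658 × √(N/4), with N − 3 degrees of freedom. Power is the probability that a noncentral t exceeds the two-sided 5% critical value.

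**The plan's figure.** Multiplying the unadjusted requirement by 1 − .65² = .5775 gives 63 × .5775 = 36.4 (normal approximation) or 64 × .5775 = 37.0 (exact t). At 36 per group, power is .786 by noncentral t and .797 by normal approximation. The stated 36 is within rounding and is not disputed.

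**Power at the numbers expected.**

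| N with outcome data | λ | Power (t) | Power (normal) | Detectable d at .80 (t) |
|---|---|---|---|---|
| 70 | 2.752 | .774 | .786 | .516 |
| 66 | 2.673 | .749 | .762 | .532 |
| 63 | 2.611 | .729 | .743 | .545 |
| 60 | 2.548 | .707 | .722 | .559 |

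**Splitting the gap.** With no attrition, 35 per group already gives .774, which is 2.6 points under .80. That part comes from 35 versus 36, rounding, and t versus normal. Attrition then costs:

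- N = 66: .774 − .749 = 2.5 points
- N = 63: .774 − .729 = 4.5 points
- N = 60: .774 − .707 = 6.7 points

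**Dependence on r at 60–66.** Power is .66–.71 at r = .60, .71–.75 at r = .65 and .76–.80 at r = .70.

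**Further covariates.** Reaching .80 at N = 63 needs a total covariate R² of about .51. The pre score alone gives .65² = .42. The plan gives no correlation from which the attention bias contribution could be judged.

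**Intent to treat.** If every enrolled participant had an observed outcome and the effect stayed at .50, power would be the N = 70 value, .774. Three things can lower it:

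- *Timing of losses, and what imputation recovers.* Outcomes were removed at random and imputed from condition and pre score (20 imputations, 4,000 runs). Intent-to-treat power was .73, .71 and .68 at 5, 10 and 15% loss, against .73, .72 and .69 for completers in the same runs. Imputation from baseline alone restores essentially nothing. If losses come after post, post scores recover part of the follow-up loss. How much depends on the post-to-follow-up correlation, which the plan does not give.
- *Dilution.* If dropouts are assessed but gain no benefit, the average effect falls to .475, .450 or .425 at 5, 10 or 15%. Power at N = 70 is then .73, .68 or .64.
- *Both together.* The plan gives nothing from which to combine them.

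**The case against.** The strongest defence is that the plan's claim is conditional and modest. It offers r = .65 as an example, says only that 35 is close to 36, adds covariates to raise power, and discloses attrition elsewhere. Moving r from .65 to .70 changes power by about as much as the attrition does. The sample is capped by the parent trial, and the detectable effect moves only from .516 to .532–.559, which is still medium. All of this is fair, and it makes the point one of disclosure. It does not remove the mismatch, because r = .65 is the only basis given for the claim and the benefit of the other covariates is not quantified.

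The timing objection also stands in part. The 5–15% runs from pre to follow-up, while the primary hypothesis (1a) is tested at post, about eight weeks earlier. Losses by post are not stated and may be smaller.

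A reader might infer three stronger things that the documents do not support:

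- *That attrition explains the whole drop from .80 to .71.* It does not; 2.6 points are present at 35 per group with no loss.
- *That intent-to-treat power has a floor at the completer value of .71.* It does not. The simulation reached .68 and the dilution case .64, and the plan does not supply what a lower bound would need.
- *That the primary post contrast bears the full loss.* The plan does not say so.

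**Conclusion.** The power statement is wrong as written for the completer analyses. On the plan's own inputs, power for d = .50 is about .71–.75 at 60–66 with outcome data (.72–.76 by normal approximation), and .73 at the expected 63. The effect detectable with .80 power is d of about .53–.56.

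These figures apply in full to the follow-up contrast, and to the post contrast only to the extent that losses occur by then. Intent-to-treat power is no higher than about .77 on the pre-score covariate alone (.79 by normal approximation), and no lower bound can be set from the documents.

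The result rests on r = .65, two-sided .05, equal groups and no gain from covariates beyond the pre score. The shortfall is moderate, and it concerns how the trial's sensitivity is described, not its design.

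**What to change.** In Statistical Power, after the comparison of 35 with 36 per group:

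- State power of about .71–.75 and a detectable d of about .53–.56 for 60–66 with outcome data. Label these as completer figures that apply fully at follow-up, and at post only as far as losses occur by post.
- State that intent-to-treat power under multiple imputation will be no higher than about .77 on the pre-score covariate alone. Give no lower bound, and say why: it depends on the timing of losses, the information that imputation recovers, and any dilution of the effect.
- Show the dependence on r at 60–66: about .66–.71 at r = .60 and .76–.80 at r = .70.
- Note that the gain from the pre attention bias covariate is not quantified.

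Leave enrolment unchanged. The cost is a few sentences and a less favourable stated figure; no patients, visits or analyses are added.
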